4.3 SUPPORTIVE EXPLORATORY EFFICACY ENDPOINTS ANALYSES

Additional exploratory analyses will be performed in a descriptive manner for continuous endpoints Vineland-3, RBS-R, CRRI, CGI, AASP, PRAS-ASD, BAI, SSP-2, PedsQL™, and PROMIS per treatment arm comprising baseline values, (up to) week 12 values and change from baseline to (up to) week 12 values.

For endpoint CGI, analyses will be performed to get the proportion of subjects in each of the rating categories per treatment arm and per time point.

For the assessment of differences between each Alogabat group and placebo regarding the CGI-I overall score at week 12, a mixed-effects MMRM analysis incorporating data up to 12 weeks of treatment will be used to utilize all the data collected over time with consideration of the variance-covariance matrix of the repeated measures. The model will include the CGI-I overall score as the dependent variable. The effects in the model will include independent variables of the fixed, categorical effects of treatment, assessment weeks relative to the first dose of study medication (i.e., time), and treatment-by-time interaction, along with covariates of the baseline value, age at screening and IQ at baseline. Time will be treated as the repeated variable within a subject. An unstructured variance-covariance structure will be applied to model the within-subject errors.

For the primary, secondary, CRRI and CGI-I endpoints, the ANCOVA will be repeated to model change from baseline data y_{ij} of participants i, and treatment $j \in \{\text{placebo}\}\$ (reference), low dose, high dose) incorporating interactions to the model as follows:

$$y_{ij}=\mu+t_j+a_i+IQ_i+t_j*IQ_i+BL_i+\epsilon_{ij}$$

and

$$y_{ij}=\mu+t_j+a_i+IQ_i+t_j*a_i+BL_i+\epsilon_{ij}$$

where μ gives the overall endpoint mean change, followed by the fixed effect t which models the effect of treatment, age a, IQ, the interactions t^*IQ and t^*a respectively, the endpoint baseline value BL, and ε , which gives the overall error term with $N(0, \sigma_{\varepsilon}^2)$.

4.4 SAFETY ANALYSES

All safety analyses will be based on the safety analysis population.

 Table 10
 Safety Statistical Analysis Methods

Endpoint	Statistical Analysis Methods
Adverse events	The original terms recorded on the eCRF by the Investigator for AEs will be coded by the Sponsor. Adverse events will be summarized by mapped term and appropriate thesaurus level.
Clinical laboratory tests	All clinical laboratory data will be stored on the database in the units in which they were reported. Laboratory test values will be presented by tabular summaries, plots, and individual listings with flagging of abnormal results. Hereby, by default the International System of Units (SI units; Système International d'Unités) will be applied, and values will be transformed to common Roche standard reference range (following Roche Safety Lab Standardisation Guidance) where applicable.
Vital signs	Vital signs data will be presented by individual listings with flagging of values outside the normal ranges and flagging of abnormalities. In addition, tabular summaries of raw values and change from baseline will be used, as appropriate.
ECG	ECG data will be presented by individual listings. In addition, tabular summaries of raw values and change from baseline will be used, as appropriate.
Concomitant medications	The original terms recorded on the participants' eCRF by the Investigator for concomitant medications will be standardized by the Sponsor by utilizing a mapped term and appropriate drug dictionary level. Concomitant medications will be presented in summary tables and listings.
C-SSRS, Neurocognitive Battery, KSS, ESS or ESS-CHAD, and Sudden Onset of Sleep Questionnaire	Data will be presented in summary tables and listings

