1.1 OBJECTIVES AND ENDPOINTS

Table 1 Primary and Secondary Objectives

Primary Objective	Endpoint
To evaluate the efficacy of 12-week treatment with alogabat compared with placebo in treating social communication deficits in participants with Autism Spectrum Disorder (ASD)	 Change from baseline to Week 12 in the Adaptive Behavior Composite score of the Vineland[™] Adaptive Behavior Scales, Third Edition (Vineland[™]-3)
Secondary Objectives	Endpoints
To evaluate the safety and tolerability of a 12-week treatment with alogabat in 15-to 45-year-old participants with ASD	 Incidence and severity of adverse events (AEs) and serious adverse events (SAEs)

	Incidence of treatment discontinuations due to AEs Change from baseline over time and
	 Change from baseline over time and incidence of clinically relevant abnormalities in vital signs including orthostatic changes, electrocardiogram (ECG) parameters and safety laboratory values including the incidence of marked laboratory abnormalities
	 Change from baseline over time in suicide risk (using the Columbia-Suicide-Severity Rating Scale [C-SSRS])
	 Incidence of daytime sleepiness assessed with the Karolinska Sleepiness Scale (KSS), the Epworth Sleepiness Scale (ESS) or the ESS for children and adolescents (ESS- CHAD), and the Sudden Onset of Sleep Questionnaire
To evaluate the efficacy of a 12-week treatment with alogabat compared with placebo on restricted and repetitive behaviors (RRBs)	Change from baseline to Week 12 in behavior/symptoms as measured by all domains of the Repetitive Behavior Scale-Revised (RBS-R) scale
To evaluate the efficacy of a 12-week treatment with alogabat compared with placebo on social behaviors	Change from baseline to Week 12 on the Vineland-3 Socialization domain
To evaluate the efficacy of a 12-week treatment with alogabat compared with placebo on communication skills	Change from baseline to Week 12 on the Vineland-3 Communication domain

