

APPENDIX 1

LIST OF PLANNED OUTPUTS FOR EFFICACY AND SAFETY

Provisional Output Name	Population	Title	
l_ae_gloss	Safety	Glossary of Adverse Event Preferred Terms and Investigator-Specified Adverse Event Terms	
I_ae	Safety	Listing of Adverse Events	
I_ae_postdose	Safety	Listing of new onset AEs after last dose of study medication	
l_ae_disc	Safety	Listing of Adverse Events Leading to Study Treatment Discontinuation	
l_cm_gloss	Safety	Glossary of Concomitant Medication Class, Preferred Name, and Investigator-Specified Terms	
I_cm	Safety	Listing of Concomitant Medication	

l_cssrs	Safety	Columbia-Suicide Severity Rating Scale (C-SSRS)	
l_ds	Safety	Listing of Patients who Discontinued from Study	
l_dv	Safety	Listing of Major Protocol Deviations	
I_eg	Safety	Listing of ECG Data	
l_ex_ti	Safety	Listing of Drug Administration and Dosing Time	
l_mh_gloss	Safety	Glossary of Medical History Coded Terms	
I_mh	Safety	Listing of Medical History	
l_vs	Safety	Listing of Vital Signs	
t_ae_int	Safety	Adverse Events by Greatest Intensity	
t_ae_oview	Safety	Safety Summary	
t_ae	Safety	Adverse Events	
t_cssrs	Safety	Columbia-Suicide Severity Rating Scale (C-SSRS)	
t_dm	Safety	Demographic and Baseline Characteristics	
t_ds	Safety	Patient Disposition	
t_eg_cfb	Safety	ECG Parameters Change from Baseline by Visit	
t_ess_cat	Safety	Epworth Sleepiness Scale (ESS) Total Score Categories	
t_ess_cfb	Safety	Epworth Sleepiness Scale (ESS) Change from Baseline by Visit	
t_ess_chad_c at	Safety	ESS for Adolescents Sleepiness Scale (ESS-CHAD) Total Score Categories	
t_ess_chad_cf b	Safety	ESS for Adolescents Sleepiness Scale (ESS-CHAD) Change from Baseline by Visit	
t_ex	Safety	Study Treatment Exposure	
t_kss_cfb	Safety	Karolinska Sleepiness Scale (KSS) Change from Baseline by Visit	
t_lb_abn_ls	Safety	Laboratory Abnormalities (Standardised parameters)	
t_lb_abn_nls	Safety	Laboratory Abnormalities (Non-Standardised parameters)	

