t_lb_cfb_ls	Safety	Laboratory Tests and Change from Baseline by Visit (Standardised parameters)	

t_lb_cfb_nls	Safety	Laboratory Tests and Change from Baseline by Visit (Non-Standardised parameters)	
t_neuro_cfb	Safety	Neurocognitive Battery Change from Baseline by Visit	
t_sudden	Safety	Sudden Onset of Sleep Questionnaire	
t_vs_cfb	Safety	Vital Signs Change from Baseline by Visit	
l_ae_ser	Safety	Listing of Serious Adverse Events	
l_dm	Safety	Listing of Demographic and Baseline Characteristics	
l_lb_abn	Safety	Listing of Laboratory Abnormalities	
I_lb	Safety	Listing of Laboratory Data and Change from Baseline by Visit	
t_ae_pt	Safety	Adverse Events by Preferred Term	
t_ae	Safety	Adverse Events Related to Study Treatment	
t_cm	Safety	Medications Started after Baseline by Medication Class and Preferred Name	
t_cm	Safety	Medications Ongoing at Baseline by Medication Class and Preferred Name	
t_cm	Safety	Medications Completed Prior to Baseline by Medication Class and Preferred Name	
t_eg_abn	Safety	ECG Parameters outside Normal Limits Regardless of Abnormality at Baseline	
t_eg_abnbl	Safety	ECG Parameters outside Normal Limits Among Patients without Abnormality at Baseline	
t_eg_qtcf	Safety	QTcF Actual Values and Change from Baseline by Visit	
t_mh	Safety	Previous and Concurrent Medical History	
I_ae_nsaesi	Safety	Listing of Non-Serious Adverse Events of Special Interest	
t_ae_nsaesi	Safety	Non-Serious Adverse Events of Special Interest	
g_ex_hist	Safety	Histogram of Dosing Time	
g_vs_mean	Safety	Mean Plot from of Vital Sign Parameters Over Time with 95% CI	
g_vs_mean_cfb	Safety	Mean Change from Baseline Plot of Vital Sign Parameters Over Time with 95% Cl	

[figure not shown]
g_lb_mean_ls	Safety	Roche-Standardized Laboratory Data
g_lb_mean_nl s	Safety	Non-Standardized Laboratory Data
g_eg_mean	Safety	Mean Plot of ECG Parameters Over Time with 95% Cl
g_eg_mean_cfb	Safety	Mean Change from Baseline Plot of ECG Parameters Over Time with 95% CI
g_ess	Safety	ESS over Time
g_ess_cfb	Safety	ESS Change from Baseline over Time
g_kss	Safety	KSS over Time
g_kss_cfb	Safety	KSS Change from Baseline over Time
g_neuro	Safety	Neurocognitive Battery

[figure not shown]
t_vabs3_ancov	Efficacy	Vineland-3 ABC GSV Score ANCOVA no interactions
t_vabs3_ancov	Efficacy	Vineland-3 ABC GSV Score ANCOVA age interaction
t_vabs3_ancov a	Efficacy	Vineland-3 ABC GSV Score ANCOVA IQ interaction
t_vabs3_ancov a	Efficacy	Vineland-3 SOC GSV Score ANCOVA no interactions

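### Two secondary safety endpoints declared as incidences (vital-sign abnormalities including orthostatic changes, and the KSS part of daytime sleepiness) have no by-arm count in the planned outputs

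*SAP*

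**What the plan says.** SAP section 1.1, Table 1, lists among the secondary safety endpoints the change from baseline and the "incidence of clinically relevant abnormalities in vital signs including orthostatic changes". It also lists the "Incidence of daytime sleepiness assessed with the Karolinska Sleepiness Scale (KSS", together with the ESS or ESS-CHAD and the Sudden Onset of Sleep Questionnaire.

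SAP section 4.4, Table 10, gives the methods. For vital signs: "Vital signs data will be presented by individual listings with flagging of values outside the normal ranges and flagging of abnormalities", and in addition "tabular summaries of raw values and change from baseline will be used, as appropriate". For the KSS and the other sleepiness instruments: "Data will be presented in summary tables and listings".

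In the visible part of SAP Appendix 1, the vital-sign outputs are a listing, the table "Vital Signs Change from Baseline by Visit" and mean plots. The KSS outputs are the table "Karolinska Sleepiness Scale (KSS) Change from Baseline by Visit" and two over-time plots. After Table 1 the SAP does not mention orthostatic change again.

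On collection, the protocol's Schedule of Activities has vital signs and orthostatic changes taken before dosing and hourly for 3 hours afterwards at dosing visits. The KSS is taken before dosing and once at 3 to 4 hours after it.

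**The concern.** An incidence is a number of participants out of those at risk. A summary of change answers a different question, and a few participants with marked values barely move it. Blood-pressure change is discussed as a potential risk in protocol section 8.3.7.1, and daytime somnolence has its own row in protocol Table 10, so the interest here is in the affected minority. If the outputs are produced as listed, the clinical study report will have no prespecified by-arm count for vital-sign or orthostatic abnormality, and none for KSS sleepiness. Any count would then have to be built afterwards, with limits chosen once the data are known.

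**Working it through.** **Step 1. Endpoints against outputs.**

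| Measure | Declared in SAP Table 1 | Visible outputs in SAP Appendix 1 | By-arm count or category table? |
|---|---|---|---|
| Vital signs | Change and incidence | Listing, change table, mean plots | No |
| Orthostatic change | Part of the vital-sign endpoint | None | No |
| KSS | One instrument for sleepiness incidence | Change table, two over-time plots | No |
| ESS, ESS-CHAD | Further instruments for the same endpoint | Total-score category tables, change tables | Yes |
| Sudden Onset of Sleep Questionnaire | Further instrument for the same endpoint | One table | Layout not stated |
| ECG | Change and incidence | Two outside-limits tables, change tables | Yes |
| Laboratory | Change and incidence | Abnormality tables, change tables | Yes |

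The SAP gives no cut-off for an abnormal vital sign, an orthostatic change or KSS sleepiness.

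**Step 2. Arm size.** The SAP needs 84 evaluable participants and assumes 20% are not evaluable (SAP section 2.2). 84 / (1 − 0.20) = 105, which reproduces the stated total. 105 / 3 = 35 per arm.

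**Step 3. How far a few marked cases move a mean.** The shifts and SDs below are assumptions, because the documents give no SD for vital signs or KSS. Suppose k of 35 participants shift by d and the rest do not change. The arm mean then moves by k × d / 35. The standard error (SE) of the difference between two arms is SD × √(2/35).

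- Systolic fall of 20 mmHg in 3 participants: 3 × 20 / 35 = 1.7 mmHg. The SE is 1.91 for SD 8 and 3.59 for SD 15, so the shift is 0.9 to 0.5 SE.
- Systolic fall of 30 mmHg in 3 participants: 3 × 30 / 35 = 2.6 mmHg, or 1.3 to 0.7 SE over the same SDs.
- KSS rise of 4 points in 3 participants: 3 × 4 / 35 = 0.34 points. The SE is 0.36 for SD 1.5 and 0.60 for SD 2.5, so the shift is 1.0 to 0.6 SE.

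**Step 4. What a count would show.** 3/35 = 8.6%, with an exact 95% interval of 1.8% to 23.1%. The interval is wide, but the affected participants are visible and attributable to an arm.

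**Step 5. Do minimum and maximum recover the information?** SAP Table 5 puts the SD, minimum, quartiles, median and maximum in each continuous summary. An extreme value that reaches the table will show there, but the number of participants who had one will not. It may also fail to reach the table. Under SAP section 4.1 one assessment per analysis window is tabulated, the one nearest the planned day, and the rest go to listings. That rule does not say which of several same-day readings is used, so it does not separate pre-dose from hourly post-dose vital signs. In SAP Table 4, study days 56 to 70 belong to no vital-sign or KSS window.

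**The case against.** A reader might infer that the SAP reports nothing but mean changes, or that neither incidence is addressed anywhere. The documents do not support either reading.

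- The summaries carry minimum, maximum and quartiles, and abnormal vital signs are flagged in a listing from which participants could be counted by hand.
- The vital-sign endpoint has a change part, and the change table serves it.
- There is no separate KSS incidence endpoint. The sleepiness endpoint is also served by the ESS and ESS-CHAD category tables and the Sudden Onset of Sleep table.
- Adverse event tables capture some cases. Protocol Appendix 3, section 5, requires a vital-sign result to be reported when it is symptomatic, changes treatment, needs intervention or is judged clinically significant. Protocol section 8.3.6 makes somnolence above Grade 1 and sudden onset of sleep events of special interest, and tables for these are planned.
- Some Appendix 1 content is not reproduced in the text available, including a part directly after the vital-sign plots, so a missing row cannot be fully excluded. SAP Table 10 does not settle this, since its ECG row is silent on the abnormality tables that Appendix 1 contains.

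All of this narrows the point, but the gap remains. A flagged listing is not a by-arm incidence. Protocol Appendix 3 itself says that some vital-sign abnormalities are not adverse events. Under its section 11, the sponsor does not derive adverse event reports from participant-reported data, and protocol Table 9 has high-functioning adults complete the KSS themselves. The ESS asks about the past month or the time since the last visit, whereas the KSS asks about the last 5 minutes and is timed to 3 to 4 hours after dosing. The orthostatic component has no visible output at all.

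**Conclusion.** The point holds in a limited form. The visible plan contains no by-arm count or percentage of participants with vital-sign or orthostatic abnormalities, no orthostatic variable, and no count by KSS category. Both are declared as incidences or as part of one, and the comparable ECG, laboratory and ESS measures have such tables. The change part of the vital-sign endpoint is served, and the sleepiness endpoint is partly served by other instruments and by event tables.

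No actual incidence can be calculated from the documents. The illustration shows only that three marked cases in an arm of 35 can move a mean by 0.5 to 1.3 SE under the assumed shifts and SDs. Safety is reported descriptively here, so the loss is one of visibility and not of a formal test. The conclusion assumes that no relevant row sits in the unreproduced part of Appendix 1.

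**What to change.** Add two by-arm tables to SAP section 4.4 and Appendix 1.

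1. **Vital signs.** Number and percentage of participants with any post-dose vital-sign abnormality and, separately, any orthostatic abnormality. Use all scheduled and unscheduled post-dose readings, not only the one selected per window. Derive the orthostatic variable as standing minus supine. Apply the same limits as the listing flags. The sponsor should set and state these, including those for orthostatic change, before unblinding.
2. **KSS.** Category counts before dosing and at the 3 to 4 hour reading, by visit, plus each participant's highest post-dose score across visits, mirroring the planned ESS category table. Counts at each of the nine scores need no cut-off. If scores are grouped, the sponsor should state the grouping before unblinding.

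The cost is two tables, one derived variable and a written statement of the flag limits. No new data are needed. If an unreproduced Appendix 1 row already provides either table, it is enough to name it in section 4.4 with its limits.

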4.4.1 Extent of Exposure

A summary will be produced showing the treatment duration in days, the total cumulative number of doses and the total cumulative dose in mg per treatment arm. A histogram binned by hours will be produced showing the distribution of dosing times per treatment arm.

4.5 OTHER ANALYSES

4.5.1 Summaries of Demographics and Baseline Characteristics

Demographics and baseline characteristics data such as baseline values of relevant scales, medical history including medications and treatments, support person status, educational status of participant and parents, etc. will be summarized by treatment, age cohort, and IQ cohort.

Additional listings, summary tables of descriptive statistics, frequency tables, and corresponding graphs will be provided as appropriate.

4.5.2 Pharmacokinetic Analyses

For all participants, plasma concentrations of Alogabat will be presented descriptively by dose and age group.

Nonlinear mixed effects modeling will be used to analyze the sparse sampling dose versus concentration versus time data collected for Alogabat. The PK data collected in this study will be pooled with data from other clinical studies conducted with Alogabat. Population and individual PK parameters such as clearance and volume of distribution will be estimated, and the influence of various covariates such as age, gender, and body weight, on these parameters will be investigated, as appropriate. Secondary PK parameters will be derived from the model as appropriate. The results of the PopPK analysis will be reported separately from the CSR.

Subjects excluded from the PK Analysis Population will be documented in a listing.

Depending on results it will be decided post hoc after database lock whether analyses will be performed that investigate the participant's exposure to Alogabat, and whether correlations of exposure to Alogabat exist with selected efficacy, PD, biomarkers and safety endpoints.

4.5.3 Biomarker Analyses

Resting state EEG is recorded up to five times per patient: Pre-baseline, day 1 pre-dose, day 1 post-dose, week 2 post-dose (optional recording) and week 12 post-dose. EEG beta power is defined as the total power in the 13-30 Hz range averaged over the fronto-central channels Fz and Cz.

To estimate pharmacodynamic effects, beta power for post-dose recordings are normalized with baseline beta power to estimate relative change. Baseline beta power is defined as the average of the pre-baseline and day 1 pre-dose values. For each post-dose recording (day 1, week 2, week 12) and dose level, the mean change and SD of change will be reported. Additionally, two-tailed two sample t-tests comparing placebo to

each treatment arm will be performed for each post-dose recording. Hereby the null-hypothesis of no difference in beta power with Alogabat treatment compared to placebo will be rejected if the p-value resulting from a two-sided t-test is < 0.1.

It will also be examined whether baseline beta power predicts clinical response. The hypothesis is that clinical efficacy increases as beta power decreases (patients with lower baseline beta power benefit more from alogabat than patients with higher baseline beta power). To this end beta power is normalized with power outside the beta range. The Baseline value is defined as the average of the pre-baseline and day 1 pre-dose values. The Pearson correlation coefficient between baseline beta power and change from baseline clinical efficacy scores will be computed for each active treatment arm and placebo. For active treatment arms the p-value will be derived from a two-sided test with null-hypothesis: r = 0. The null hypothesis will be rejected if the two-sided p-value is < 0.2. The test will be performed for the clinical efficacy endpoints Vineland-3 ABC GSV composite, Vineland-3 Socialization GSV composite, RBS-R total, and CRRI total.

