8.7.1.3 Pharmacodynamic Biomarkers: Assessments of Neurophysiological Effects

The PD biomarker assessments comprise resting state EEG and SPV (measured by means of EOG recorded during an oculomotor task). These assessments will be performed at the timepoints specified in the SoA (Section 1.3). Resting state EEG will be acquired in alternating 1 min blocks of eyes open and eyes closed while participants sit relaxed, following the recommendations of the International Pharmaco-EEG Society (Jobert et al 2012). Resting state data will be processed off-line to derive the beta power (12 to 30 Hz). During the oculomotor task, participants will be instructed to look at and follow a target stimulus on the screen, which switches horizontally from the screen center to either side at fixed amplitudes. Participants' head movements will be reduced by means of a chin rest. The system will be initially calibrated to establish the conversion between EOG signals and eye movement amplitude. EOG data will be analyzed off-line to derive saccadic peak velocities.

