4.2 PRIMARY, SECONDARY AND EXPLORATORY EFFICACY ANALYSIS

The primary efficacy analysis evaluates the mean change from baseline to 12 weeks of treatment as measured by the Vineland-3 ABC three-domain GSV composite. The difference in the mean change from baseline between each of the two active doses and placebo will be extracted as contrasts from the ANCOVA model.

The efficacy analyses of the secondary endpoints and of the CRRI total score evaluate the mean change from baseline to 12 weeks of treatment. The difference in the mean change from baseline of the two active doses and placebo will be extracted as contrasts from the ANCOVA model.

The efficacy analysis of CGI-I evaluates the overall score at 12 weeks of treatment. The difference of the two active doses and placebo will be extracted as contrasts from the ANCOVA model.

4.2.1 Definition of Primary Endpoint

The primary endpoint is Change from baseline to Week 12 in the Adaptive Behavior Composite score of the Vineland[™] Adaptive Behavior Scales, Third Edition (Vineland[™]-3), as defined in Section 1.1 of SAP (see Table 1).

4.2.2 Main Analytical Approach for Primary, Secondary, CRRI and CGI-I Endpoints

The analyses of primary, secondary, CRRI and CGI-I efficacy endpoints will include all participants in the Efficacy Analysis Population.

An analysis of covariance (ANCOVA) model will be used to compare treatment effects for the primary, secondary, CRRI and CGI-I efficacy endpoints across the overall Efficacy Analysis Population of adolescents and adults. The model will include treatment as main effect, individual age at screening, IQ, and baseline score as covariates. Treatment differences will be estimated together with their 80% confidence intervals as derived from the model and their associated p-values.

The ANCOVA model will be applied to change from baseline data y_{ij} of participants i, and treatment $j \in \{\text{placebo (reference)}, \text{low dose}, \text{high dose}\}\)$ as follows:

$$y_{ij}=\mu+t_i+a_i+IQ_i+BL_i+\epsilon_{ij}$$

where μ gives the overall endpoint mean change, followed by the fixed effect t which models the effect of treatment, age a, IQ, the endpoint baseline value BL, and ϵ , which gives the overall error term with $N(0, \sigma_{\epsilon}^2)$.

Table 8 Efficacy Statistical Analysis Methods

Endpoint	Statistical Analysis Methods
Primary	ANCOVA
Secondary	
CRRI, CGI-I	

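### EEG beta power is compared with placebo by unadjusted t-tests on baseline-normalised values; a baseline-adjusted ANCOVA would be at least as precise in large samples and needs no new data

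*SAP*

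**What the plan says.** SAP 4.5.3 (Biomarker Analyses) sets out the pharmacodynamic analysis of resting-state EEG:

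- **Outcome scale:** "beta power for post-dose recordings are normalized with baseline beta power to estimate relative change". It does not say whether this is a ratio, a percentage change or a log ratio.
- **Baseline:** "Baseline beta power is defined as the average of the pre-baseline and day 1 pre-dose values".
- **Test:** "two-tailed two sample t-tests comparing placebo to" each treatment arm, at each post-dose recording. The null hypothesis "will be rejected if the p-value resulting from a two-sided t-test is < 0.1". No covariate, log transform or supporting model is mentioned.
- **Recordings:** Day 1 post-dose, then "week 2 post-dose (optional recording) and week 12 post-dose".

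For the primary, secondary, CRRI and CGI-I endpoints, SAP 4.2.2 uses ANCOVA instead: "The model will include treatment as main effect, individual age at screening, IQ, and baseline score as covariates". SAP 1.2.1 says that randomisation was stratified by age and IQ.

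In the protocol, beta power is an exploratory endpoint (Section 3, Table 6), and Section 9.4.5 plans only listings and descriptive summaries for pharmacodynamic biomarkers. The SAP therefore adds the test.

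The band is defined in two ways. SAP 4.5.3: "EEG beta power is defined as the total power in the 13-30 Hz range". Protocol 8.7.1.3: "derive the beta power (12 to 30 Hz", with the same 12 to 30 Hz range in Table 6.

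**The concern.** Dividing by baseline is, on the log scale, a change score: it fixes the baseline slope at one whether or not the data support that value. Where the true slope is below one, noise in the baseline recordings passes into the outcome. ANCOVA estimates the slope, so in large samples its error variance is never larger. The planned test also ignores the two stratification factors, age and IQ.

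What is at stake is the chance of detecting a real pharmacodynamic effect. Beta power is the only such marker with a planned comparison against placebo in the SAP; no test is given for saccadic peak velocity. The usable sample may also be small: the Week 2 recording is optional, and SAP 3 excludes recordings made too long after the last dose or after missed doses. If the clinical result is null, an imprecise pharmacodynamic comparison is less help in interpreting it.

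**Working it through.** **The plan's own figure.** None exists for EEG: no SD, correlation, effect size or power is stated. The only sized comparison is Vineland-3 (SAP 2.2): 28 evaluable per arm, difference 4.5, SD 8.0, one-sided alpha 0.10. The standard error is 8 × √(2/28) = 2.138, and power = Φ(4.5/2.138 − 1.282) = 79.5%, which agrees with the stated 80% to within a point. Only the 28 per arm is carried over, as an assumption.

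**Variances on the log scale.** Assume equal variance 1 at each recording, correlation r between the post-dose recording and each baseline recording, and rbb between the two baseline recordings. The mean of the two baselines has variance vB = (1 + rbb)/2. Then:

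- change score: 1 + vB − 2r
- ANCOVA: 1 − r²/vB
- difference: (vB − r)²/vB, which is never negative and is zero when r = vB.

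This treats the baseline as a mean of logs, whereas the SAP averages power, so it is an approximation. It also leaves out any gain from age and IQ, for which the documents give no information.

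**Separate correlations**, r from 0.5 to 0.9 and rbb from 0.7 to 0.95 (assumed):

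| r | rbb | vB | Change | ANCOVA | Reduction |
|---|---|---|---|---|---|
| 0.5 | 0.95 | 0.975 | 0.975 | 0.744 | 24% |
| 0.5 | 0.7 | 0.850 | 0.850 | 0.706 | 17% |
| 0.7 | 0.85 | 0.925 | 0.525 | 0.470 | 10% |
| 0.9 | 0.9 | 0.950 | 0.150 | 0.147 | 2% |
| 0.9 | 0.8 | 0.900 | 0.100 | 0.100 | 0% |

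The range over the grid is 0 to 24%.

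**One common correlation** (r = rbb = ρ). Take an effect that gives the t-test 80% power at two-sided 0.10 with 28 per arm: (1.645 + 0.842) × √(2/28) = 0.665 SDs of change. ANCOVA power is then Φ(2.487/√ratio − 1.645), where ratio is ANCOVA variance over change variance.

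| ρ | Variance ratio | SE reduction | ANCOVA power |
|---|---|---|---|
| 0.5 | 0.889 | 5.7% | 84.0% |
| 0.7 | 0.941 | 3.0% | 82.1% |
| 0.8 | 0.963 | 1.9% | 81.3% |
| 0.9 | 0.982 | 0.9% | 80.6% |

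With a single baseline recording the ratio would be (1 + ρ)/2, a reduction of 25% at ρ = 0.5 and 5% at ρ = 0.9. Averaging two recordings already recovers more than half of that.

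**Simulation** (three arms of 28, log-normal power, assumed log-SD 0.5, baseline as the only covariate):

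| ρ | t-test, raw relative change | t-test, log ratio | ANCOVA, log power |
|---|---|---|---|
| 0.5 | 75.9% | 79.3% | 82.9% |
| 0.7 | 77.6% | 79.1% | 81.2% |
| 0.9 | 79.0% | 79.4% | 80.0% |

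Type I error was about 0.09 to 0.10 for all methods. If the SAP means raw relative change, part of the loss comes from that scale.

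**Band.** The share of 12 to 30 Hz power lying between 12 and 13 Hz is ln(13/12)/ln(30/12) = 8.7% if the spectrum falls as 1/f, and (1/12 − 1/13)/(1/12 − 1/30) = 12.8% if it falls as 1/f². Both spectral shapes are assumptions.

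**The case against.** The strongest reply is that this is a modelling preference on an exploratory endpoint. The t-test is valid under randomisation, the two-recording baseline already removes much of the noise, and if beta power is highly reproducible almost nothing is lost. Every figure above depends on correlations that the documents do not give, and some plausible pairs show no gain. An exploratory biomarker need not share the clinical model, and nothing shows that age or IQ predicts change in beta power. Pooling three arms also assumes a common error variance, whereas separate comparisons with placebo do not borrow the other dose's variance. All of this stands. It limits the point to an inexpensive improvement; it does not make the t-test the better choice.

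A reader might infer three stronger points that the documents do not support:

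- **That the test is biased or inflates false positives.** It does not; the simulated type I error is at or slightly below the nominal 0.10.
- **That this comparison is the trial's main evidence of target engagement.** The protocol does not call it that. Section 4.2.3.1 reports that a response on this measure and on saccadic peak velocity was already shown in study BP40091, and Section 2.2.5 lists a completed PET study of the target receptor.
- **That pooling three arms brings an important gain in degrees of freedom.** Going from 28 + 28 − 2 = 54 to 84 − 6 = 78 moves the two-sided 0.10 critical value only from 1.674 to 1.665, about 0.5%.

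**Conclusion.** The point holds as a minor matter of efficiency. The planned comparison is valid but fixes the baseline slope and leaves collected covariates unused, so it can lose some precision. The reduction in error variance available from log-scale ANCOVA is 0 to 24% over the separate-correlation grid and about 2 to 11% with a common correlation of 0.5 to 0.9. These ranges rest on assumed correlations, equal variances, 28 complete recordings per arm and large-sample formulas. Where the gain is zero, estimating the extra coefficients could make ANCOVA very slightly less precise in a sample of this size. The skewness of raw ratios is likewise a modelling assumption, because the SAP does not say which form of relative change is tested.

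The two band definitions are a real inconsistency. It needs no assumption to establish, but it is a separate and minor matter that adds no weight to the case for ANCOVA.

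**What to change.** In SAP 4.5.3, replace the t-tests with an ANCOVA at each post-dose recording: log post-dose beta power on treatment (three arms), log of the averaged baseline beta power, age and IQ. Report each active arm as a back-transformed ratio to placebo with its confidence interval, and keep the two-sided 0.1 threshold. This also settles which scale is tested.

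The cost is SAP wording and one model in place of the t-tests. There is a small downside: the reported effect becomes a ratio of geometric means, and the three arms share one error variance. Keep the planned descriptive mean and SD of relative change by arm so that the simpler quantity stays visible.

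Separately, state one beta band in both documents, or record in the SAP that the lower limit was changed and why.
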